### **13.1 Sample Size, Power and Significance Levels**

A total of 186 patients will be randomized to one of four treatment groups (GWP42003-P 10 mg/kg/day, GWP42003-P 20 mg/kg/day, placebo 10 mg/kg/day dose volume equivalent, or placebo 20 mg/kg/day dose volume equivalent) at a 2:2:1:1 ratio. The randomization will be stratified by age group (2–5 years, 6–12 years and 13–18 years). The placebo groups will be pooled for the analyses of efficacy.

For a Wilcoxon–Mann–Whitney test comparing two distributions with a two-sided significance level of 0.05, a sample size of 62 per group is required to obtain a power of at least 80%. This is based on a gamma distribution for the GWP42003-P groups with scale parameter of 65.614 and shape parameter of 1.0886, and a gamma distribution for the placebo group with scale parameter of 40.887 and shape parameter of 2.3059.

Maximum likelihood estimates using the Newton–Raphson approximation were computed for the scale and shape parameters using data from study GWEP1332 Part B.

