#### **3.2 Definition of Sample Size**

A total of 186 patients will be randomized to one of 4 treatment groups (GWP42003-P 10 mg/kg/day, GWP42003-P 20 mg/kg/day, placebo 10 mg/kg/day dose volume equivalent, or placebo 20 mg/kg/day dose volume equivalent) at a 2:2:1:1 ratio. The randomization will be stratified by age group (2–5 years, 6–12 years and 13–18 years). The placebo groups will be pooled for the analyses of efficacy.

For a Wilcoxon–Mann–Whitney test comparing 2 distributions with a 2-sided significance level of 0.05, a sample size of 62 per group is required to obtain a power of at least 80%. This is based on a gamma distribution for the GWP42003-P groups with scale parameter of 65.614 and shape parameter of 1.0886, and a gamma distribution for the placebo group with scale parameter of 40.887 and shape parameter of 2.3059.

Maximum likelihood estimates using the Newton–Raphson approximation were computed for the scale and shape parameters using data from study GWEP1332 Part B.

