### 5.5.2 Primary Efficacy Endpoint

The primary endpoint is the change in convulsive seizure frequency during the treatment period (see Section 5.1.3.3) of the study compared to baseline (see Section 5.1.3.1) in patients taking GWP42003-P compared with placebo.

The primary endpoint will be analyzed using negative binomial regression on the sum of the convulsive seizure counts during the treatment period. However, convulsive seizure frequency (28-day average) and percentage change in seizure frequency will be presented using summary statistics. Percentage change from baseline in convulsive seizure frequency will be calculated as:

$$\frac{[(\text{Frequency during the treatment period} - \text{Frequency during baseline}) \div \text{Frequency during baseline}] \times 100}{}$$

The frequency during each period will be based on 28-day averages and calculated as:

$$(\text{Number of seizures in the period} \div \text{Number of reported days in IVRS in the period}) \times 28$$

For convulsive seizure endpoints only, if patients are randomized with no convulsive seizures during the baseline period then the percentage change from baseline will be calculated as:

---

(Frequency during the treatment period + 1) × 100

A mixed effect model with repeated measures will be performed modelling the observed number of convulsive seizures in the baseline period and treatment period implemented within the framework of general linear models using the negative binomial response distribution. The model will include stratified age group (2–5 years, 6–12 years and 13–18 years), time, treatment arm and treatment arm by time interaction as fixed effects and patient as a random effect. The log transformed number of days in which seizures were reported will be included as an offset. The time variable corresponds to an indicator for the baseline period and treatment period.

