The GLIMMIX procedure in SAS will be utilized to perform the analysis with the option maxopt=300 applied. If the model fails to converge, then the statement 'nloptions tech=nr ridge;' will be added. If convergence is still not achieved then 'method=laplace' will be utilized. However, if convergence is still not possible, then the model will be changed to utilize the log normal response distribution (log rate model). If the log rate model is required and there are patients with a seizure frequency during the baseline or treatment period of 0 then all patients will have their baseline and treatment period seizure frequency adjusted by adding a value of 1.

The estimated ratio of least squares means for treatment period to baseline period and 95% confidence intervals (CIs) will be presented for each treatment arm. In addition, the estimated ratio of each GWP42003-P group to placebo and 95% CIs will be presented along with the p-value testing the null hypothesis that this ratio is 1.

For each ratio and upper and lower bound of the 95% CI, the percentage reduction will also be presented, calculated as:

$$[1 - (X \div Y)] \times 100\%$$

Where X corresponds to the treatment period estimate, or GWP42003-P ratio, and Y corresponds to the baseline period estimate, or placebo arm ratio.

Primary efficacy analysis will be performed using ITT analysis set.

For a period of time, the limit for the number of daily seizures for each seizure type recorded in IVRS was 99. A >99 seizure log was added to the CRF to allow the capture of the exact number of seizures where the count on a particular day was >99. When deriving the seizure frequencies, the count >99 provided on the CRF will replace the recorded 99 seizures in IVRS for the corresponding seizure type. This will only be done when the corresponding IVRS record was exactly 99.

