#### **5.5.5 Subgroup Analyses**

To assess the degree of effect heterogeneity, effect modifier analyses are proposed, on the ITT analysis set, for the primary efficacy endpoint and the key secondary efficacy endpoint of  $\geq 50\%$  reduction in convulsive seizure frequency.

For the primary efficacy endpoint, the effect modifier analysis will be performed using the negative binomial regression analysis as described in Section 5.5.2. The model will be updated to include covariates for each level of the effect being tested (excluding a reference level), individually and with interactions with time, interactions with treatment arm and interactions with time and treatment. A separate model will be used for testing each effect. The treatment ratios (GWP42003-P vs. placebo), percent reduction and 95% confidence intervals will be presented for each level of the effect. In addition, the effect by time by treatment arm interaction p-value, testing the hypothesis that the effect level treatment ratios are homogeneous, will be presented.

For the key secondary efficacy endpoint of  $\geq 50\%$  reduction in convulsive seizure frequency, patients with a  $\geq 50\%$  reduction in seizure frequency will be modelled using logistic regression, including stratified age group and treatment arm as covariates. The model will also include covariates for each level of the effect being tested (excluding a reference level), individually and with interactions with treatment arm. A separate model will be used for

testing each effect. The number and percent of responders, and odds ratios and 95% confidence intervals will be presented for each level of the effect. In addition, the effect by treatment arm interaction p-value, testing the hypothesis that the effect level odds ratios are homogeneous, will be presented.

The following effects will be tested:

- Age group (2-5 years, 6-12 years and 13-18 years). Note: stratified age group will be removed as a covariate for this model.
- Sex (Male, Female).
- Region (US, Rest of the World).
- Clobazam use (Yes, No).
- Valproic acid use (Yes, No).
- Stiripentol use (Yes, No).
- Clobazam use and Stiripentol use (Yes/Yes, Yes/No, No/Yes, No/No).
- Levetiracetam use (Yes, No).
- Topiramate use (Yes, No).

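### The age-group main effect in the primary model has almost no influence on the arm-by-time test, so the primary comparison is in effect not adjusted for the randomisation stratum; the test stays valid and is at worst somewhat conservative

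*SAP*

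**What the plan says.** Age group, in three levels, is the only stratification factor named (SAP 3.2, Protocol 7.2 and 13.1).

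SAP 5.5.2 and Protocol 13.6.2 describe the same primary model. After age group it lists "time, treatment arm and treatment arm by time interaction as fixed effects and patient as a random effect", and log reported days is the offset. There are two time levels: "The time variable corresponds to an indicator for the baseline period and treatment period". The inferential output is defined as follows: "the estimated ratio of each GWP42003-P group to placebo and 95% CIs will be presented along with the p-value testing the null hypothesis" that the ratio equals 1. Each group's ratio is treatment period over baseline, so the tested parameter is the arm-by-time term. No age-by-time term is listed. If the negative binomial fit fails after two further attempts at convergence, the response distribution becomes log normal.

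Elsewhere age does act on the comparison:

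- The rank, log and percentage-change ANCOVAs carry age group as a covariate (SAP 5.5.2.1).
- The 50% responder test is a CMH test stratified by age group (SAP 5.5.3.1.2).
- The effect-modifier models enter each factor "individually and with interactions with time, interactions with treatment arm and interactions with time and treatment" (SAP 5.5.5).

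**The concern.** A reader of SAP 5.5.2 would take the primary test to be adjusted for the stratum because age group is in the model. But age group does not change between the two periods. Its main effect shifts a patient's expected log rate equally in both, and the patient intercept already allows for differences in level. Only a term that lets the change from baseline vary by age would adjust the tested contrast.

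The stake is precision. Stratified randomisation balances age across arms, so omitting age-related change introduces no bias. If the change does differ by age, however, that variation is left in the residual and the SE is too large. The model carries Tests 1 to 4 of Table 3 (primary endpoint and total seizures), and failure at any test stops those below it. Non-convulsive seizures and individual seizure types use the same model.

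**Working it through.** **1. The plan's own power figure.** Protocol 13.1 states "two-sided significance level of 0.05, a sample size of 62 per group is required to obtain a power of at least 80" per cent, for an unadjusted Wilcoxon–Mann–Whitney test. The planning gammas are scale 65.614, shape 1.0886 (active) and scale 40.887, shape 2.3059 (placebo). They give P(active < placebo) = 0.6432. Noether's formula gives total N = (1.960 + 0.842)² / [12 × 0.25 × (0.6432 − 0.5)²] = 127.5, or 63.8 per group. Simulated power at 62 per group is 79.9% (40,000 runs). The figure reproduces, and age plays no part in it.

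**2. Algebra for the log-rate fallback.** For patient i in period t (0 = baseline, 1 = treatment):

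Y_it = μ + α_age + β_arm + t(τ + γ_arm) + u_i + e_it

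D_i = Y_i1 − Y_i0 = τ + γ_arm + (e_i1 − e_i0)

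Both α_age and u_i cancel. Because β_arm is unrestricted, all information on γ comes from D. With both periods observed, the age main effect therefore cannot alter the estimate of γ or, for a given covariance matrix, its SE.

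A numerical check used one generated data set, with arms deliberately unbalanced within age and the covariance held fixed. The contrast is −0.5367 without age and −0.5367 with the age main effect. The SE is 0.1783 both ways under compound symmetry and 0.2255 both ways under an unstructured covariance. With age by time the contrast becomes −0.5110.

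**3. Negative binomial mixed model.** Assumptions, none of which the documents give: baseline rate 14 per 28 days before the rule of at least four seizures; between-patient log SD 1.0; dispersion 0.3; age shares 30/45/25%; age gradient in baseline level 0.3 per step; 10% short follow-up. N = 186, no treatment effect, 300 trials per setting, maximum likelihood by quadrature.

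| Age gradient in log change, per step | No age term, mean SE | Age main effect (as planned), mean SE | Age by time added, mean SE |
|---|---|---|---|
| 0 | 0.1475 | 0.1474 | 0.1467 |
| 0.3 | 0.1540 | 0.1535 | 0.1471 |

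- Effect of the age main effect: the estimate moves by 0.024 and 0.037 SE on average (largest 0.15 SE), the mean SE ratios are 0.9998 and 0.997, and 1 of 600 decisions changes.
- Effect of adding age by time: the SE falls by 1 − 0.1467/0.1474 = 0.5% and 1 − 0.1471/0.1535 = 4.2%. No decisions change with no gradient, and 4 of 300 change at 0.3.
- Rejection under the null with the planned model is 5.0% and 1.3%. The Monte Carlo SE at 5% is about 1.3 points.

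A separate set of simulations (150 trials per setting, 62 per arm, Laplace fit) gave SEs of 0.148 → 0.147 with no gradient, 0.153 → 0.147 at ±0.3 and 0.163 → 0.147 at ±0.5. The last is a fall of 1 − 0.147/0.163 = 9.8%. Two data sets at 0.6 per step gave 0.164 → 0.147, which is indicative only.

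**4. What the SE means for the test.** If the true sampling SD is 0.147 and the reported SE is 0.153, the actual two-sided level is 2Φ(−1.96 × 0.153/0.147) = 4.1%. With a reported SE of 0.163 it is 3.0%.

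Power is approximated by Φ(|log ratio|/SE − 1.96). The documents state no effect on this scale, so a range is shown. The planning gammas, if read as proportional to seizure frequency (an assumption), give log ratios of −0.28 for means (71.4/94.3), −0.46 for medians and −0.57 for geometric means.

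| Log ratio | SE 0.147 | SE 0.153 | SE 0.163 |
|---|---|---|---|
| −0.28 | 48% | 45% | 40% |
| −0.46 | 88% | 85% | 81% |
| −0.57 | 97% | 96% | 94% |

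The loss is 1 to 3 points at ±0.3 and 3 to 7 points at ±0.5. The formula treats the reported SE as the true SD. Where that SE is inflated and power is above 50%, it overstates the loss slightly.

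**The case against.** Several points on the other side stand.

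- **Validity is untouched.** A significant result from the planned model remains valid; any error is towards conservatism.
- **The gradient is assumed.** Precision is lost only if age predicts change over 14 weeks, and neither document quantifies that. Protocol 3.1 says convulsive seizures decline after age five, but that concerns level over years, which a main effect can represent. The assumed gradients are also large: ±0.3 is exp(0.6) = 1.8-fold between youngest and oldest strata, and ±0.5 is exp(1.0) = 2.7-fold.
- **Other analyses adjust for age.** The ANCOVAs, the CMH test and the age effect-modifier model will show whether age matters. They do not alter the p-value that Table 3 uses for Test 1.
- **Extra terms have a cost in sparse models.** Individual seizure types exclude patients without that type at baseline (SAP 5.5.3.2.4). A failed fit there can end in a different response distribution.

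A reader might infer that the age main effect cannot act at all. That is exact only for the log-rate model. In the negative binomial model a little comes through the non-linear weights. With a much steeper assumed age gradient in baseline level (1.0 per step, dispersion 0.4), two exploratory data sets showed shifts of up to 0.43 SE.

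A reader might also infer that the trial falls short of its stated 80% power. The documents do not support this, because that figure is for an unadjusted rank test.

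**Conclusion.** The point holds as one about efficiency. The stratification factor is named in the primary model, but in a form that leaves the tested contrast unchanged (log-rate fallback) or nearly unchanged (negative binomial model under moderate assumptions). The test is in effect unadjusted for the randomisation stratum.

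There is no bias and no inflation of type I error. The size of any loss is unknown from the documents: practically nothing if age is unrelated to change, and a reported SE about 4% to 11% too large (0.153/0.147 and 0.163/0.147) under assumed gradients of 0.3 and 0.5 log units per step. No single power figure can be attached, since the plan states no effect size on this scale.

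The direction follows from the algebra and is secure. The magnitudes rest on the assumed variance, dispersion and gradients, and on maximum likelihood fits. SAP 5.5.2 reserves the Laplace method for its third attempt, so its first-line GLIMMIX fit was not itself simulated.

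**What to change.** Before unblinding, add age group by time as a fixed effect (2 df) to the primary model in SAP 5.5.2 and Protocol 13.6.2, and so to the total and non-convulsive seizure models that refer to it. For individual seizure types, add the term only where the model converges, and state that the term is dropped before any move to the log-normal distribution, so that it cannot itself trigger that fallback. Record the change in SAP 5.8.

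An alternative is to model the treatment-period count with log baseline frequency and age group as covariates. That is a larger change to the primary analysis.

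The cost is one model term, a matching edit to both documents after the blinded data review meeting, and a convergence rule for the sparse models. If age is unrelated to change, the primary SE is the same to within 0.001. The sample size needs no revision.

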### 5.5.2.1 Sensitivity Analyses for the Primary Efficacy Endpoint

The following sensitivity analyses will be conducted for the primary endpoint:

- Primary endpoint analysis repeated using the PP analysis set.
- Wilcoxon rank-sum test on percentage change from baseline in convulsive seizure frequency during the treatment period. An estimate of the median differences between each GWP42003-P group and placebo, together with approximate 95% CIs, will be calculated using the Hodges–Lehmann approach.
- A rank analysis of covariance (ANCOVA) on percentage change from baseline in convulsive seizure frequency during the treatment period.

The ranks of the percentage change from baseline and the baseline convulsive seizure frequency will be calculated. The rank of the percentage change from baseline will then be analyzed using an ANCOVA model with the rank of the

baseline convulsive seizure frequency and age group (2–5 years, 6–12 years and 13–18 years) as covariates and treatment group as a fixed factor. The estimated least squares means, treatment differences, together with the 95% CIs and p-values will be presented.

- ANCOVA of log transformed convulsive seizure frequency during the treatment period.

The convulsive seizure frequency during the treatment period and the baseline convulsive seizure frequency will be log transformed prior to analysis. The log transformed convulsive seizure frequency during the treatment period will then be analyzed using an ANCOVA model with the log transformed baseline convulsive seizure frequency and age group as covariates and treatment group as a fixed factor. The back transformed estimated treatment ratios, together with the 95% CIs and p-values will be presented.

If there are any patients with no seizures during the baseline or treatment periods, then 1 will be added to the convulsive seizure frequency for all patients prior to log transformation.

- ANCOVA on percentage change from baseline in convulsive seizure frequency during the treatment period including baseline and age group as covariates and treatment group as a fixed factor. The estimated least squares means, treatment differences, together with the 95% CIs and p-values will be presented.
- Primary endpoint analysis repeated using the maintenance period (see Section 5.1.3.4) rather than the treatment period.

This analysis will include only patients who have at least 7 days of seizure data within the maintenance period.

- Primary endpoint analysis repeated using each 4 weeks of the maintenance period (Week 1–4, Week 5–8 and Week 9–12 of the 12-week maintenance period).

This analysis will include only patients who have at least 7 days of seizure data within each corresponding 4-week period rather than the treatment period.

- Primary endpoint analysis repeated using the worst case of last observation carried forward (LOCF), next observation carried backward (NOCB) and the daily mean from the non-missing data for each patient (rounded up to the nearest integer) to impute missing data arising from unreported days in IVRS during the treatment period only (not the baseline period).

Any intermittent missing data for the number of convulsive seizures arising from unreported days in IVRS will be imputed using the worst (highest number of seizures) of the following for each patient: LOCF, NOCB and the mean daily number of seizures during the treatment period (rounded up to the nearest integer) based on using non-missing data:

$$\text{Number of seizures} \div \text{Number of reported days in IVRS}$$

- Wilcoxon rank-sum test on percentage change from baseline in convulsive seizure frequency during the treatment period, using multiple imputation (MI) to impute data under the Missing Not at Random (MNAR) assumption (see Section 5.5.2.1.1).
- Primary endpoint analysis repeated using the safety analysis set.

### 5.5.2.1.1 Sensitivity Analysis of Missing Data

Missing data in this trial could potentially arise from the mechanism of MNAR. In order to understand the impact on the trial findings from missing data under the MNAR assumption, sensitivity analyses of the primary endpoint will be carried out for the ITT analysis set by multiple imputations on convulsive seizure frequency, based on time-points corresponding to each 14 days of the treatment period. The final period will consist of 15 days to include Day 99, if applicable.

For each 14 calendar days of the treatment period (15 days for the final period), the convulsive seizure frequency will be calculated as:

$$\left[ \frac{\text{Number of convulsive seizures in the period}}{\text{Total number of reported days in IVRS for all combined periods (maximum of 99 days)}} \right] \times 28$$

For patients with any periods with no reported days in IVRS, the total number of reported days in IVRS will include an additional 14 days for each missing period. For example, if a patient withdraws with 80 reported days in IVRS from 6 of the 7 14-calendar-day periods, then the total number of reported days in IVRS for the above calculation will be the sum of 80 and 14, i.e. 94 days.

Intermittent missing values for intermediate nominal visits before the last nominal visit will be imputed using the MCMC method in PROC MI with an IMPUTE=MONOTONE statement for 100 times for each treatment group separately. The resulting 100 partially imputed datasets will have a monotone missing pattern and will be further imputed under an MNAR assumption that the imputed value for the missing efficacy data of GWP42003-P patients (discontinued for certain reasons) are similar to, worse than, or better than those of placebo patients for the following 2 scenarios:

- (1) MNAR assumed for missing values resulting from discontinuation due to AEs in the GWP42003-P groups and Missing at Random (MAR) for others, including other patients discontinued in the GWP42003-P groups and patients in placebo group;
- (2) MNAR assumed for missing values resulting from discontinuation due to any reason or any other monotone missing data in the GWP42003-P groups and MAR for others, including patients in placebo group.

For each of the 2 scenarios above, imputation will be carried out once on each of the 100 imputed datasets using the SAS MI procedure (with the 100 imputed datasets included in the 'BY' statement of the MI procedure) as follows:

- Step 1: Monotone missing data under the MAR assumption at treatment period time-point t will be imputed by means and covariance from the observed convulsive seizure frequency at baseline and at each treatment period time-point up to time-point t (in chronological order) in their corresponding treatment groups (i.e., patients in the GWP42003-P groups whose missing data are assumed to be MAR and all patients in the placebo group). The imputation will be realized using the MI procedure with the 'MONOTONE REG' option, for each treatment group separately. The imputation model will include baseline convulsive seizure frequency and each treatment period time-point up to time-point t (in chronological order).
- Step 2: With the data imputed from Step 1, monotone missing data of patients in the GWP42003-P groups under the MNAR assumption will be imputed. At each treatment period time-point t, the input dataset for the MI procedure will include all placebo patients and those patients from each GWP42003-P group that have values missing under MNAR at that time-point. The imputation model will include convulsive seizure frequency at baseline and each treatment period time-point up to

time-point  $t$  (in chronological order). After the sequential imputation is completed for all time-points, the imputed values at time-point  $t$  plus, a sensitivity parameter,  $k \times$  standard error of the observed convulsive seizure frequency in the placebo group at the corresponding time-point (calculated using the denominator of the total number of reported days in IVRS for all combined periods, as given above) will then form the final imputed values. The sensitivity parameter  $k$  (where, for example,  $k = 0, \pm 0.5, \pm 1.0, \pm 1.5$ , etc.) will be used to explore the robustness of the estimated treatment difference to the degree of decrease or increase (positive values of  $k$  represent decrease and negative values represent increase) in MNAR efficacy from the placebo patients.

After missing values at all the time-points are imputed, the overall percentage change from baseline in convulsive seizure frequency will be calculated as:

$$\left[ \frac{\text{The sum of the frequencies of each 14 days of the treatment period} - \text{Frequency during baseline}}{\text{Frequency during baseline}} \right] \times 100$$

If the sum of the frequencies of each 14 days of the treatment period becomes less than zero, as a result of imputation, then the percentage change from baseline in convulsive seizure frequency will be set to  $-100\%$ .

The data will then be analyzed using a Wilcoxon rank-sum test.

The results of the Wilcoxon rank-sum test on the 100 imputed datasets will be combined to derive an overall p-value. The test statistic will be based on the method provided by Rubin and a modified macro from Mogg.

For each analysis, the increment in the positive value of  $k$  will stop once the overall p-value is greater than 0.05. The decrease in the negative values of  $k$  will continue until the overall p-value becomes smaller than the p-value from the primary efficacy analysis, for the corresponding Dose Level.

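### In the missing-not-at-random analysis, days lost inside a period cut by withdrawal get no imputation and no k shift, and the negative-k search stops against the p-value of a different test

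*SAP*

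**What the plan says.** SAP 5.5.2.1.1 divides the treatment period into seven periods: six of 14 days and a last one of 15 ("The final period will consist of 15 days to include Day 99, if applicable"). Each period's frequency is its own seizure count divided by "Total number of reported days in IVRS for all combined periods (maximum of 99 days"), times 28. The denominator is thus the patient's whole reported time, not the days in that period.

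A period counts as missing only if it is empty. For patients with "any periods with no reported days in IVRS, the total number of reported days in IVRS will include an additional 14 days" per missing period. The worked example is this: "if a patient withdraws with 80 reported days in IVRS from 6 of the 7 14-calendar-day periods", the denominator is 80 + 14 = 94.

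Missing periods are imputed in sequence, using baseline and the preceding periods as predictors. For patients on active treatment whose data are assumed missing not at random, the imputed value plus k times a placebo standard error "will then form the final imputed values". That standard error is "calculated using the denominator of the total number of reported days in IVRS for all combined periods". Positive k means worse efficacy than placebo patients, negative k better.

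The completed data are tested with a Wilcoxon rank-sum test pooled over 100 imputations. On one side, "the increment in the positive value of $k$ will stop once the overall p-value is greater than 0.05". On the other, "The decrease in the negative values of $k$ will continue until the overall p-value becomes smaller than the p-value from the primary efficacy analysis" for that dose level. SAP 5.5.2 defines the primary analysis as negative binomial regression.

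Protocol 13.6.2.1 chose the 14-day grid and the Wilcoxon test, and left the full details to the SAP.

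**The concern.** The section exists to show how far the result depends on data lost to withdrawal. Two of its rules work against that.

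**Rule 1, the cut period.** Few patients will withdraw exactly at a period boundary. A period with a single reported day counts as observed, so the rest of it is neither imputed nor shifted. Those days take, by default, the patient's own average over observed and imputed days. The cut period also enters the imputation of later periods as a low value, although it is low because it was cut short. The number most likely to be quoted is the k at which significance is lost. If some of the lost days never receive the shift, that k comes out too large.

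**Rule 2, the negative-k stop.** Two different tests on the same data give different p-values even when nothing is missing. A search that ends when one falls below the other partly measures the gap between the tests.

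**Working it through.** **Inputs.** Periods 1–6 are 14 days each and period 7 is Days 85–99 (SAP 5.5.2.1.1). The treatment period ends at the last dose or Day 99 (SAP 5.1.3.3). There are 62 patients per group (SAP 3.2). Assumptions: every day up to withdrawal on Day w is reported, and withdrawal days are spread evenly. The documents give no withdrawal numbers or days.

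**1. The SAP's example.** 80 + 14 = 94, as stated. If it is read as withdrawal on Day 80, the 99 − 94 = 5 uncounted days are Days 81–84 of period 6, plus one day because the 15-day last period is credited with 14.

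**2. Lost days without imputation or shift.** For withdrawal on Day w these are (last day of the cut period − w).
- Each 14-day period, summed over its withdrawal days: 13 + 12 + … + 0 = 91.
- Last period, Days 85–98: 14 + 13 + … + 1 = 105.

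| Withdrawal days | Unshifted | All lost days | Share | Factor on k |
|---|---|---|---|---|
| 1–98 | 6 × 91 + 105 = 651 | 98 × 99/2 = 4,851 | 13.4% | 4,851/4,200 = 1.155 |
| 15–98 | 5 × 91 + 105 = 560 | 84 × 85/2 = 3,570 | 16% | 3,570/3,010 = 1.19 |

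The factor is all lost days divided by shifted lost days. It takes the standard error as equal across periods. For single patients the unshifted share runs from 0% (withdrawal at the end of periods 1–6) through 13/28 = 46% (Day 71) to 100% (Days 85–98).

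**3. The predictor.** At one seizure per day, a full period of a completer has the value 14/99 × 28 = 3.96. After withdrawal on Day 71, period 6 has the value 1/85 × 28 = 0.33 (denominator 71 + 14 = 85), and period 7 is imputed from it.

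**4. Size and sign at k = 0.** Take a constant rate and exact imputation of empty periods. Relative to the truth, the patient's total is w/(w + 14 × empty periods) + (days in empty periods)/99.
- Day 15: 15/85 + 71/99 = 0.894, which is 10.6% too low.
- Day 30: 30/86 + 57/99 = 0.925, which is 7.5% too low.
- Day 80: 80/94 + 15/99 = 1.003, slightly too high.
- Days 85–98: w/w = 1, no bias.
- Average over Days 15–98: 2.1% too low, with Day 15 the largest. Average over Days 1–98: 2.7% too low.

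Now let the rate change around withdrawal:
- Observed rate 1.25 times the later rate, withdrawal on Day 80: the SAP rule gives 100/94 + 15/99 = 1.215, against (100 + 19)/99 = 1.202 on all days. The SAP rule is too high.
- Rate tripled on Days 29–33, then withdrawal, later days at the earlier rate: 43/89 + 57/99 = 1.059, against (43 + 9 + 57)/99 = 1.101. The SAP rule is too low.

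**5. The negative-k stop.** With 62 against 62, the standard deviation of the Wilcoxon U is √(62 × 62 × 125/12) = 200. Moving one patient from mid-rank to the lowest rank changes U by 31, so z changes by 31/200 = 0.155. The outcome is floored at −100%, so three such patients can move z by at most 3 × 0.155 = 0.47. If the negative binomial p-value lies beyond that reach, no k ends the search. If the Wilcoxon p-value is already the smaller one at k = 0, the search ends before it starts.

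**The case against.** The best case for the plan has four parts.

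*The grid is the protocol's, and leaving unreported days out matches the primary model's offset.* True, and neither the grid nor the Wilcoxon test is an error. But the primary model does not claim to shift lost days, and this analysis does. The worst-case rule for unreported days in SAP 5.5.2.1 belongs to a different analysis and does not fill the gap.

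*Rule 1 does not always favour the drug.* This stands. A reader might infer that mid-period withdrawals always look better than they should. Step 4 shows otherwise: there is no bias for Days 85–98 at a constant rate, and there can be an upward error for late withdrawals after worsening.

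*The practical effect may be small.* This stands in part. Simulation with 3, 6 or 12 assumed active-arm withdrawals gave tipping-k ratios of 1.28, 1.36 and 1.43, and a reader might take these as the true inflation. They rest on assumed withdrawal numbers, days and within-patient variability, none of which the documents give. In a rerun on the same assumptions, only 4%, 8% and 18% of trials significant at k = 0 tipped by k = 1.5, the largest value the SAP names as an example. The day-count factor needs fewer assumptions and is the one to rely on.

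*Negative k only explores outcomes favourable to the drug, and a Wilcoxon comparator would not cure everything.* Both are true. With the Wilcoxon p-value of Table 8.2.2 as comparator, the rerun still ended at k = 0 in 34%, 29% and 17% of trials, although non-stopping nearly vanished (2%, 0%, 0.3%). Such percentages are fragile: with other stand-ins for the primary test, the share ending at k = 0 ran from 7% to 94%. That argues for a fixed grid, not for leaving the rule alone.

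**Conclusion.** Both rules are wrong as written and should be changed. Nothing else in the SAP repairs them.

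Rule 1 leaves 13.4% (withdrawal Days 1–98) to 16% (Days 15–98) of lost days outside the shift, which makes the tipping k about 1.16 to 1.19 times too large. This assumes evenly spread withdrawals, full reporting up to withdrawal and equal standard errors by period. At k = 0 the effect is small, 2.1% too low on average over Days 15–98 at a constant rate, and no general direction can be claimed.

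Rule 2 makes the reported negative k hard to interpret and can leave the search without an end. The positive-k stop uses 0.05 and has no such mismatch of tests.

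A reader might go on to doubt the primary result. The documents do not support that: both rules act only inside this sensitivity analysis, and the primary test and its type I error are untouched.

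**What to change.** Amend SAP 5.5.2.1.1 before unblinding.

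1. **Cut periods.** Compute each period's frequency on its own reported days and use these rates as predictors. In a period cut by withdrawal, keep the observed days and impute the unobserved days under the same missing-at-random or not-at-random rule as that patient's later periods. Use the completed rate as the predictor for later periods. Apply k times the standard error in proportion to the unobserved days, with the standard error on the same own-days scale. Combine periods by calendar days: 14 each, 15 for the last, 99 in total. For a wholly missing 14-day period k keeps its present size, because (count/14 × 28) × 14/99 = count/99 × 28.

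2. **Negative k.** Replace the stopping rule with a fixed k grid stated in advance. If a comparator is kept, use the Wilcoxon p-value of Table 8.2.2, and note that the search may still end at k = 0.

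**Cost.** SAP wording and one extra step in the sequential imputation; no new data. A rate imputed for a few days borrows the residual variance of a 14-day rate, so its noise is slightly understated. The second change is a matter of wording.
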